### 9.1 Enrolment Visit

After the site staff has checked the eligibility criteria, the informed consent will be retrieved as described in section 13.3 and the following information will be collected:

- Demographic data: age, sex, height, weight
- Inclusion and non-inclusion criteria verification
- Medical history: past and current diseases (if relevant for the study) including allergies
- Indication for the vascular embolization procedure: number of lesions to be treated, lesion type and location
- Therapeutic/palliative strategy for the lesions to be treated: previous procedure, and if a second vascular embolization procedure using Lipiodol® Ultra Fluid in association with surgical glues is scheduled within the next 30 days after the first one, the next procedure scheduled after study procedure(s), target percent obliteration for the first study procedure (evaluated according to 4 level-score: 1. <50%; 2. 50-75%; 3. 75-99%; and 4. 100% corresponding to a complete nidus obliteration rate)
- Safety information: adverse event(s) whether serious or not. For more information on safety reporting, refer to Section 10
- Concomitant medications

### 9.2 First Study procedure

The study procedure is a vascular embolization using Lipiodol® Ultra Fluid in association with surgical glue (the mixture) via selective arterial catheterization.

Site staff will collect the following information related to the first study procedure:

- The conditions of mixture administration: date of the procedure, time of first injection of the mixture, associated surgical glue (brand name), puncture site, time leaving the catheterization laboratory, number of injections, and per injection : concerned lesion, ID number of IMP, mixture ratio of Lipiodol® Ultra Fluid to surgical glue, total volume, catheter flush if any (yes/no)
- Changes in therapeutic/palliative strategy introducing additional embolization material
- Post-procedure obliteration (evaluated according to 4 level-score: 1. <50%; 2. 50-75%; 3. 75-99%; and 4. 100% corresponding to a complete nidus obliteration rate) per lesion assessed on

 CONFIDENTIAL	Protocol No. LUF-44-001 Version No. 3.0 Date January 20 th 2017	Page 25 / 43
---	--	--------------

earliest available angiogram after the first embolization procedure (e.g. DSA, CTA, MRA, US, Doppler US)

- Safety information: adverse event(s), whether serious or not. For more information on safety reporting, refer to Section 10
- Concomitant medications

### 9.3 Second study procedure (optional)

According to the patient need and health status, a second vascular embolization using Lipiodol® Ultra Fluid in association with surgical glue may be considered by the investigator within the next 30 days after the first one.

In this case, this procedure will be considered as a second study procedure and the following will be recorded:

- Date and reason (adverse event, completion of study disease therapeutic/palliative strategy)
- Concerned lesions to be treated including new lesions, and target percent obliteration for the second procedure
- The condition of mixture administration: time of first injection of the mixture, associated surgical glue (brand name), puncture site, time leaving the catheterization laboratory, number of injections, and per injection : concerned lesion, ID number of IMP, mixture ratio of Lipiodol® Ultra Fluid to surgical glue, total volume, catheter flush if any (yes/no)
- Changes in therapeutic/palliative strategy introducing additional embolization material
- Post-procedure obliteration (evaluated according to 4 level-score: 1. <50%; 2. 50-75%; 3. 75-99%; and 4. 100% corresponding to a complete nidus obliteration rate) per lesion assessed on earliest available angiogram after the second study procedure (e.g. DSA, CTA, MRA, US, Doppler US)
- Safety information: adverse event(s), whether serious or not. For more information on safety reporting, refer to Section 10
- Concomitant medications

### 9.4 Safety follow-up at one month

Collection of data relevant to the safety follow-up of the subject is expected at 30 +/- 3 days after the last procedure using Lipiodol® Ultra Fluid associated with surgical glues

Safety follow-up is expected when at least one administration of the mixture Lipiodol® Ultra Fluid in association with surgical glues will occur.

The following information will be collected by the site:

- Date and kind of follow-up (visit, phone, medical records)
- New therapeutic/palliative procedure if any within the period, administered to the subject for the study disease: Date, type (embolization using other material, surgery, radiosurgery, other) and reason (adverse event, completion of study disease therapeutic/palliative strategy).
- Safety information: adverse event(s), whether serious or not. For more information on safety reporting, refer to Section 10
- Concomitant medications

 CONFIDENTIAL	Protocol No. LUF-44-001 Version No. 3.0 Date January 20 th 2017	Page 26 / 43
---	--	--------------

## 10 SAFETY REPORTING

### 10.1 Adverse Event

#### 10.1.1 Definition of Adverse Event

An Adverse event (AE) is any untoward medical occurrence in a clinical study subject administered a medicinal product and which does not necessarily have a causal relationship with this treatment.

An adverse event can therefore be any unfavourable and unintended sign (including an abnormal laboratory finding, for example), symptom, or disease temporally associated with the use of a medicinal product, whether or not considered related.

#### 10.1.2 Recording/Collection of Adverse Events

The Investigator or his/her designee will invite the subject to report any abnormality experienced as part of the usual clinical follow-up.

All AE, whether considered as related or not to the administration of the mixture of Lipiodol® Ultra Fluid and surgical glues and/or the study procedure of vascular embolization should be reported in the medical file and the CRF and followed up from onset to resolution or stabilization of sequelae. If no follow-up is performed, the investigator must provide a justification.

In order to ensure complete safety data collection, all AEs occurring during the time of the subject's participation in the study, must be reported and followed. As reminder the subject's participation is defined as the period from written informed consent to the last study observation and defined in Section 11.

The following safety information must be collected by the investigator using the same procedure as AEs: medication errors and uses outside what is foreseen in the protocol, including misuse and abuse of the product, suspicion of transmission of an infectious agent via the product, reactions resulting from an occupational exposure, unusual failure in efficacy, overdose (symptomatic or not), all reports of pregnant or breastfeeding women exposure even if uneventful, all reports of suspected drug-drug interaction with another product (symptomatic or not).

In the context of the study, overdose is defined as a total volume of Lipiodol® Ultra Fluid administered of 15mL during a procedure of vascular embolization using Lipiodol® Ultra Fluid in association with surgical glues.

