7. Subject previously treated with Interleukin II as described in Lipiodol® Ultra Fluid Summary of Product Characteristics
8. Subject currently treated with effective anticoagulant therapy
9. Pregnant or breast-feeding female subject
10. Subject having received any investigational medicinal product within 7 days prior to enrolment
11. Subject with anticipated, current or past condition (medical, psychological, social or geographical) that would compromise the subject's safety or her/his ability to participate to the study
12. Subject unlikely to comply with the protocol, e.g. uncooperative attitude, and unlikely to complete the study
13. Subject related to the Investigator or any other study staff or relative directly involved in the

 CONFIDENTIAL	Protocol No. LUF-44-001 Version No. 3.0 Date January 20 th 2017	Page 4 / 43
---	--	-------------

Study Title: Safety and Efficacy of Lipiodol® Ultra Fluid in Association with Surgical Glues during Vascular Embolization, a phase IV study		
EU PAS register number: EUPAS15045		
Study product: Lipiodol® Ultra Fluid (480 mg I/ml), solution for injection	Active Ingredient(s): Ethyl esters of iodized fatty acids of poppy seed oil (Lipiodol® Ultra Fluid)	study conduct
Investigational Medicinal Product(s) administration		

The product investigated is Lipiodol® Ultra Fluid used in association with surgical glues, together referred to as “mixture”. The glue should be chosen according to the investigator and site practice and knowledge. The mixture should be administered via selective arterial catheterization only.
 
The dose of Lipiodol® Ultra Fluid administered during the embolization procedure depends on lesion size. The Lipiodol® Ultra Fluid and the surgical glue mixture may vary from 20 to 80% but usually consists of a 50/50 mixture.
 
The volume of Lipiodol® Ultra Fluid injected should not exceed 15 ml during the procedure of vascular embolization.
		
Study duration		

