### 5.3 Condition of Investigational Medicinal Product Administration

Lipiodol® Ultra Fluid will be administered in association with surgical glues.

Commercially available surgical glues will be used by the sites according to the investigator choice and usual practice. Brand name of the surgical glues used and applicable SmPCs will be collected.

Vascular embolization with liquid agents is a complex and delicate technique which should only be performed by trained physicians in an appropriate medicosurgical setting.

A premature polymerisation reaction may exceptionally occur between Lipiodol Ultra Fluid and certain glues or batches of glues. Prior to any use of new batches of Lipiodol® Ultra Fluid or glue, it is mandatory that investigators verify *in vitro* and document the compatibility between the glue used and Lipiodol Ultra-Fluid.

The dose of Lipiodol® Ultra Fluid administered during the embolization procedure depends on lesion size. The Lipiodol® Ultra Fluid and liquid embolizing agent (surgical glue) mixture may vary from 20 to 80% but usually consists of a 50/50 mixture.

The Lipiodol® and surgical glue mixture should be administered via **selective arterial catheterization only**.

Guerbet    CONFIDENTIAL	Protocol No. LUF-44-001 Version No. 3.0 Date January 20 th 2017	Page 20 / 43
--	--	--------------

The volume of Lipiodol® Ultra Fluid injected should not exceed 15 ml during each procedure of vascular embolization.

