### **10.3.2 Adverse Events of Special Interest**

An AE of Special Interest (AESI) is an AE designated by Guerbet for transmission to Pharmacovigilance in the same time frame as an SAE.

There are no AESI defined for this study.

 CONFIDENTIAL	Protocol No. LUF-44-001 Version No. 3.0 Date January 20 th 2017	Page 32 / 43
---	--	--------------

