#### Protocol deviations

As per ICH E3 guideline, a protocol deviation is any change, divergence, or departure from the study design or procedures defined in the protocol, with or without impact to the patient safety or the efficacy assessments. Protocol deviations are displayed in the Clinical Study Report (CSR) as a metric of the feasibility and reliability of the study. The list of protocol deviations is presented in the table below and can be updated if necessary. Protocol deviations will be gathered from monitoring files and clinical database.

Of note, if the reason of deviations is related to the COVID pandemic then it will be indicated in the Statistical Data Review Meeting Minutes (DRM) and the corresponding deviation presented apart.

The deviations are listed in the table below:

Category	Description	Source
Inclusion criteria not met/	Inclusion criteria n°01 not met	Clinical data base
Non-inclusion criteria met	Inclusion criteria n°02 not met	Monitoring
	Inclusion criteria n°03 not met	Clinical data base
	Inclusion criteria n°04 not met	Monitoring
	Inclusion criteria n°05 not met	Clinical data base
	Non-inclusion criteria n°01 met	Monitoring
	Non-inclusion criteria n°02 met	Clinical data base
	Non-inclusion criteria n°03 met	Monitoring
	Non-inclusion criteria n°04 met	Monitoring
	Non-inclusion criteria n°05 met	Monitoring
	Non-inclusion criteria n°06 met	Clinical data base
	Non-inclusion criteria n°07 met	Clinical data base
	Non-inclusion criteria n°08 met	Clinical data base
	Non-inclusion criteria n°09 met	Monitoring
	Non-inclusion criteria n°10 met	Monitoring
	Non-inclusion criteria n°11 met	Monitoring
	Non-inclusion criteria n°12 met	Monitoring
	Non-inclusion criteria n°13 met	Monitoring

Category	Description	Source
Forbidden concomitant medication	Concomitant medication significantly impacting safety (Beta-blockers, Metformin, Interleukin II)	Clinical data base
	Concomitant medication with effective anti-coagulant therapy	Clinical data base
IMP deviation	Temperature excursion for IMP	Monitoring
	IMP management not appropriate	Monitoring
	Volume of Lipiodol® Ultra Fluid > 15 mL	Clinical data base
	Lipiodol and surgical glue mixture not administered via selective arterial catheterization	Monitoring
Missing data	Age is missing	Clinical data base
	Sex is missing	Clinical data base
	Weight is missing	Clinical data base
	Height is missing	Clinical data base
	Medical history is missing	Clinical data base

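### Does a 15 mL overdose definition without a comparator clash with the 15 mL limit in a way that requires a change to the plan?

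*Protocol*

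**What the plan says.** Four places refer to a Lipiodol volume of 15 mL in one procedure.

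- **Protocol synopsis**, product administration: "The volume of Lipiodol® Ultra Fluid injected should not exceed 15 ml during the procedure of vascular embolization".
- **Protocol 5.3**: "The volume of Lipiodol® Ultra Fluid injected should not exceed 15 ml during each procedure of vascular embolization".
- **SAP 5.2**, table of protocol deviations, sourced from the clinical database: "Volume of Lipiodol® Ultra Fluid > 15 mL".
- **Protocol 10.1.2**: "overdose is defined as a total volume of Lipiodol® Ultra Fluid administered of 15mL during a procedure of vascular embolization".

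The last sentence determines what sites record. Protocol 10.1.2 introduces a list with "The following safety information must be collected by the investigator using the same procedure as AEs". The list includes overdose, with or without symptoms, and also "medication errors and uses outside what is foreseen in the protocol". Protocol 10.3.2 adds: "There are no AESI defined for this study".

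**The concern.** The limit in the synopsis and in Protocol 5.3 is inclusive, so 15.0 mL is allowed. The SAP's deviation rule is strict, so 15.0 mL is not a deviation. The overdose sentence names 15 mL itself. One procedure at exactly 15.0 mL would then be permitted, compliant and an overdose.

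This is the only definition of overdose in the documents, and sites are told to collect overdoses even when nothing happened to the subject. Two sites with identical 15.0 mL procedures could record them differently, each claiming to follow the protocol. In a study whose primary objective is safety, inconsistent safety labels deserve a check. If they reached the primary criterion or a planned table, the count of affected subjects could depend on how each site read one sentence.

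**Working it through.** There is no sample size, power or error rate to reproduce here: Protocol section 8 plans no hypothesis or test. The check is one of logic.

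**Inputs.** Let *v* be the total Lipiodol volume in one procedure, in mL.

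- Within the limit (synopsis, Protocol 5.3): *v* ≤ 15.
- Deviation (SAP 5.2): *v* > 15.
- Overdose as literally worded (Protocol 10.1.2): *v* = 15.
- Two readings that supply a comparator: *v* > 15, or *v* ≥ 15.

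**Classification of test volumes**

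| *v* (mL) | Within limit | SAP deviation | Overdose, literal | Overdose if > | Overdose if ≥ |
|---|---|---|---|---|---|
| 10.0 | yes | no | no | no | no |
| 14.9 | yes | no | no | no | no |
| 15.0 | yes | no | **yes** | no | **yes** |
| 15.1 | no | yes | **no** | yes | yes |
| 20.0 | no | yes | **no** | yes | yes |
| 30.0 | no | yes | **no** | yes | yes |

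Bold cells disagree with the limit and the deviation rule.

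**What the table shows**

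1. The limit and the deviation rule are exact complements and agree at every volume.
2. The literal overdose wording disagrees at 15.0 mL and at every volume above it. The misfit is therefore not confined to one value on the literal reading.
3. With a strict sign, all three rules agree throughout. With an inclusive sign, a mismatch remains at 15.0 mL only. The documents do not settle which was meant.

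**How far the label travels**

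- *Primary criterion* (Protocol 7.1, SAP 2.3.1 and 5.6.2.1). It counts subjects with an adverse event judged related to the mixture, between first injection and leaving the catheterization laboratory. Volume and overdose status do not enter.
- *Planned safety tables* (SAP 5.6.2). None in the visible text is defined by overdose.
- *Volumes above 15 mL*. These are collected under Protocol 10.1.2 as use outside the protocol and flagged under SAP 5.2 from recorded data, whatever a site calls them.
- *Expedited route*. No event of special interest is defined, and overdose is not listed among the issues for immediate reporting in Protocol 10.2.1.
- *Exposure* (SAP 5.6.1). The Lipiodol volume is calculated per injection. Summing over the injections of a procedure (the SAP's categories run to 6) gives *v* directly, so any site label can be compared with the actual volume.

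**Upper bound.** A subject has at most 2 study procedures, so at most 2 × 1 = 2 uncertain labels. The documents give no distribution of volumes, so no frequency can be derived. Protocol 5.2 describes the product unit as one 10 mL ampoule. Since 15 / 10 = 1.5, reaching 15.0 mL takes a second ampoule in the same procedure. Protocol 5.2 mentions a second unit only for a second procedure, although Protocol 5.4 and the per-injection recording of unit numbers in 9.2 leave room for more than one.

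**The case for a change.** The best case for acting is that this sentence is an instruction to sites, not background. It cannot be applied as worded, because the reader has to supply a comparator, and one of the two plausible choices leaves the clash at 15.0 mL. Other comparison signs did survive in the text, for example the lowest obliteration category in the Protocol and the deviation threshold in the SAP, so a lost sign cannot be taken for granted.

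There is also a conditional route into the analysis. SAP 5.6.2 treats an adverse event with missing relationship as related to the mixture unless it began before the first procedure. An overdose entry stored as an adverse event, with causality blank and an onset time inside the laboratory, would count as a reaction in the primary window.

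The wording point stands: as read, the sentence is incomplete. The extraction point stands only as uncertainty, since survival of some signs neither proves nor excludes loss of this one. The analysis route needs several conditions together: a procedure at exactly 15.0 mL, a site that labels it overdose, storage of that label as an adverse event, and a blank causality field. Collecting an item by the same procedure as adverse events does not establish that it is stored or counted as one. Protocol 10.1.1 reserves that term for an untoward medical occurrence. Should such an entry appear, ordinary data review would expose it against the calculated volume.

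**Conclusion.** The concern does not call for a change to the plan. The overdose sentence as read does not fit the limit or the deviation rule, but this is a clerical weakness, possibly produced by PDF reading, and following the plan is not shown to give a wrong result. Its reach is at most two uncertain labels per subject at one volume, once the sentence is read with either comparator. The volumes that breach the limit are captured by two other routes.

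This rests on three assumptions: sites read the sentence together with the limit in Protocol 5.3 rather than as meaning exactly 15 mL; overdose labels without an event are not counted as reactions; and the redacted part of the SAP holds no overdose analysis. If the source page carries no sign, the synopsis, Protocol 5.3, Protocol 10.1.2 and SAP 5.2 are for the sponsor's clinical and pharmacovigilance functions to reconcile as a matter of drafting. I take no position on which threshold is right, and the statistical analysis does not depend on it.

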#### 10.1.3 Description of Adverse Events

The following guidelines and definitions should be used by the investigator for the description of an AE when reporting information:

- **Nature of AE:** preferably an overall diagnosis or syndrome, rather than individual symptoms or signs. The investigator must report AE using standard medical terminology. The same terms should be used in the source documentation and in the CRF.
- **Date and time of onset:** date and clock time of the AE start
- **Intensity:**
  - Mild: the subject is aware of the sign or symptom, but it does not interfere with her/his usual daily activities and/or it is of no clinical consequence

- Moderate: the AE interferes with the usual daily activities of the subject or it is of some clinical consequence
- Severe: the subject is unable to work normally or to carry out his/her usual daily activities, and/or AE is of definite clinical consequence.
- **Date of the event end** (or consolidation): The real date of event end will be entered if the event has come to its end before the date of end of subject's follow-up. If the AE is still ongoing by the time of end of study follow-up for the subject, the subject should be followed-up until AE resolution or a justification should be provided by the Investigator (e.g. chronic disease or subject lost to follow-up) in the medical file.
- **Causal relationship to the mixture of Lipiodol® Ultra Fluid and surgical glue :**
  - Related: the definition of adverse reaction implies a reasonable possibility of a causal relationship between the event and the mixture. This means that there are facts (evidence) or arguments to suggest a causal relationship.
  - Not related: Applicable when no mixture has been administered (pre-administration period) or when no causal relationship exists between the mixture and the event, but an obvious alternative cause exists (e.g. the subject's underlying medical condition or concomitant therapy).

All AEs assessed as related to the mixture will qualify as ADRs in the evaluation of primary and secondary criteria, as described in section 7.
- **Causal relationship to the study procedure of vascular embolization :**
  - Related
  - Not related
- **Outcome:**
  - Recovered/Resolved: the AE is no longer present at any intensity.
  - Recovered/Resolved with sequelae: the AE is resolved but residual effects are still present.
  - Not recovered/Not Resolved: the AE is still present at the last contact with the subject.
  - Fatal: this AE caused or directly contributed to subject's death.
- **Action taken with regard to administration of the mixture:**
  - No action: for AE occurring during the pre-treatment/procedure or post-treatment/procedure period, or if the mixture dosing/administration remained the same in spite of AE being present.
  - Study products withdrawn: the mixture was not administered or was stopped.
- **Other action taken:**
  - AE-targeted medication: the subject took a medication (either prescription or non-prescription) specifically for this AE. The medication(s) should be reported in the appropriate section of the CRF ("concomitant drug" section)
  - Other AE-targeted action: subject used other therapeutic measures (e.g. ice, heating pad, brace, cast...) or subject underwent a procedure (physiotherapy, additional laboratory test...) for this AE. The therapeutic measure(s) should be reported in the appropriate section of the CRF ("Action other than drug administered for the AE" section)
- **Assessment of the seriousness of the AE:** see Section 10.2 for serious adverse event (SAE) definition.

 CONFIDENTIAL	Protocol No. LUF-44-001 Version No. 3.0 Date January 20 th 2017	Page 28 / 43
---	--	--------------

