## 7 EVALUATION CRITERIA

### 7.1 Primary Criterion

The primary evaluation criterion is the number and percentage of subjects experiencing adverse drugs reactions (ADRs) occurring during the course of each vascular embolization procedure after administration of Lipiodol® Ultra Fluid in association with surgical glues and before catheterization laboratory discharge.

Adverse events (AEs) will be collected during subject participation to the study, i.e. from written informed consent until end of the follow-up period. Site investigators will be required to assess the causal relationship to the mixture of Lipiodol® Ultra Fluid associated with surgical glues as described in section 10.1.3. All AEs assessed as related to the mixture of Lipiodol® Ultra Fluid and surgical glues will be qualified as ADRs.

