### 12.3 Safety Data

**Extent of exposure data** will be summarized per patient, per procedure and if necessary per administration: Number of procedures, reason for having a second procedure, subject duration of participation, number of injections, total volume and ratio of mixture, volumes of Lipiodol® Ultra Fluid and of the glues will be calculated, glues brand name, punctures sites, catheter flush done, other embolization material used and duration from first injection up to the time leaving the catheterization laboratory.

**Concomitant medication, material and procedures** administered during the subject participation will be summarized: Concomitant medications, additional embolization material introduced during study procedures and any new therapeutic/palliative procedure reported at follow-up will be

 CONFIDENTIAL	Protocol No. LUF-44-001 Version No. 3.0 Date January 20 th 2017	Page 34 / 43
---	--	--------------

summarized. Concomitant medications will be coded using the WHODrug dictionary and tabulated by ATC codes.

**Safety variables** collected for this study are the following; descriptive statistics will be performed on these data.

For the primary evaluation criterion, the following parameters will be described on adverse events related to the mixture (ADRs) occurring per study procedure(s):

- Number and percentage of subjects experiencing at least one ADR
- Number and percentage of ADRs
- Number and percentage of subjects experiencing at least one serious ADR
- Distribution by System Organ Class and preferred term (MedDRA Dictionary): number and percentage of subjects experiencing at least one ADRs and number and percentage of ADRs
- Number and percentage of ADRs according to their intensity and outcome
- Number and percentage of subjects treated for an ADR
- Number and percentage of subjects with mixture administration withdrawal due to ADRs

For the secondary evaluation criterion, ADRs descriptions will be repeated with all ADRs occurring in the whole subject participation period (Study procedure (s) and follow-up period).

Adverse events parameters will be collected as described in section [10.1.3](#) during the study procedure(s) and during the follow-up period.

For the secondary evaluation criteria related to AEs, all parameters will be described (secondary safety criteria):

- Number and percentage of AEs
- Number and percentage of subjects experiencing at least one AE

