#### 5.6.2.1 Primary analysis of the primary criteria

The following parameters will be described on ADRs occurring, per study procedure, after administration of Lipiodol® Ultra Fluid in association with surgical glues and before catheterization laboratory discharge (i.e

CONFIDENTIAL	STATISTICAL ANALYSIS PLAN N° LUF-44-001  VERSION N° 2.0	Page 18 / 29
--------------	---	--------------

ADR start date is greater or equal to time of first injection and lower or equal to time leaving the catheterization laboratory):

- Number and percentage of subjects experiencing at least one ADR,
- Number of ADRs,
- Distribution of number of ADRs per subject (1/2/3 or more),
- Number and percentage of subjects presenting with at least one ADR per intensity,
- Number of ADRs according to their intensity,
- Number and percentage of subjects presenting with at least one ADR per outcome,
- Number of ADRs according to their outcome,
- Number and percentage of subjects presenting with at least one ADR requiring an ADR-targeted medication,
- Number of ADRs requiring an ADR-targeted medication,
- Number and percentage of subjects presenting with at least one ADR requiring another ADR-targeted action,
- Number of ADRs requiring another ADR-targeted action,
- Number and percentage of subjects presenting with at least one ADR per lesion location,
- Number of ADRs per lesion location,
- Number and percentage of subjects presenting with at least one ADR per lesion type,
- Number of ADRs per lesion type,
- Number and percentage of subjects with mixture administration withdrawal due to at least one ADR,
- Number of ADRs leading to discontinuation of mixture administration,
- Number of ADRs leading to premature discontinuation,
- Number and percentage of subjects presenting with at least one serious ADR, whatever the seriousness criteria,
- Number of serious ADRs, whatever the seriousness criteria,
- Number and percentage of subjects presenting with at least one serious ADR per seriousness criteria,
- Number of serious ADRs per seriousness criteria.

The following distributions, by SOC and PT, will be tabulated on ADRs occurring, per study procedure, after administration of Lipiodol® Ultra Fluid in association with surgical glues and before catheterization laboratory discharge (i.e ADR start date is greater or equal to time of first injection and lower or equal to time leaving the catheterization laboratory):

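### The 'and/or' in the Mild intensity definition lets an event be graded Mild while it also meets Moderate or Severe, and no rule says which grade counts

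*Protocol*

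**What the plan says.** Protocol 10.1.3 gives investigators three intensity levels built on the same two features.

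- Mild opens with "Mild: the subject is aware of the sign or symptom, but" and continues "it does not interfere with her/his usual daily activities and/or it is of no clinical consequence".
- The next level reads "Moderate: the AE interferes with the usual daily activities of the subject or it is of some clinical consequence".
- The top level reads "Severe: the subject is unable to work normally or to carry out his/her usual daily activities, and/or AE is of definite clinical consequence".

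Section 10.1.3 does not say what to do when an event fits more than one level. The visible SAP text has no intensity definition or grading rule of its own.

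Intensity is then reported. Among the primary-criterion outputs, protocol 12.3 lists "Number and percentage of ADRs according to their intensity and outcome", and it lists intensity again for all AEs. SAP 5.6.2.1 has "Number and percentage of subjects presenting with at least one ADR per intensity" with a matching count of events, and repeats its outputs by surgical glue. SAP 5.6.2.4 repeats the ADR outputs for later periods and adds the same intensity tables for AEs.

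The primary criterion itself is not graded. Protocol 7.1 defines it as the "number and percentage of subjects experiencing adverse drugs reactions (ADRs) occurring during the course of each vascular embolization procedure".

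**The concern.** An either-feature rule suits a higher grade, since one bad feature is reason enough to move an event up. In the lowest grade it works the other way: one benign feature lets the event stay down. An event of definite clinical consequence that does not disturb daily activities meets Mild and Severe together. An event that stops the subject's normal activities but has no clinical consequence does the same.

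Two investigators could therefore grade the same reaction differently and both comply with the protocol. Protocol 12 restricts the study to descriptive statistics, so no later step in the analysis corrects a grade. At stake is whether the intensity tables describe severity consistently, and whether they place too many events in the lowest row.

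**Working it through.** There is no figure in the plan to reproduce; the check is a logical enumeration.

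**Inputs.** The three definitions in protocol 10.1.3. Interference takes the values none, interferes or unable. Clinical consequence takes the values none, some or definite. That gives 3 × 3 = 9 profiles. The subject is assumed to be aware of the sign or symptom, as Mild requires.

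**Rules as written.**
- Mild: interference = none OR consequence = none.
- Severe: interference = unable OR consequence = definite.
- Moderate, exclusive reading: interference = interferes OR consequence = some.
- Moderate, nested reading: any interference OR any consequence, so that unable and definite also count.

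| Interference | Consequence | Levels met (exclusive) | Levels met (nested) | Level after the fix |
|---|---|---|---|---|
| none | none | Mild | Mild | Mild |
| none | some | Mild, Moderate | Mild, Moderate | Moderate |
| none | definite | Mild, Severe | Mild, Moderate, Severe | Severe |
| interferes | none | Mild, Moderate | Mild, Moderate | Moderate |
| interferes | some | Moderate | Moderate | Moderate |
| interferes | definite | Moderate, Severe | Moderate, Severe | Severe |
| unable | none | Mild, Severe | Mild, Moderate, Severe | Severe |
| unable | some | Moderate, Severe | Moderate, Severe | Severe |
| unable | definite | Severe | Moderate, Severe | Severe |

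**Counts as written.**
- Mild is met by 3 profiles with no interference plus 3 with no consequence, less the 1 counted twice: 3 + 3 − 1 = 5 of 9.
- Only none/none is Mild alone, so 5 − 1 = 4 of 9 meet Mild and a higher level. This holds on both readings of Moderate.
- Moderate and Severe overlap without Mild in 2 profiles (exclusive) or 3 (nested).
- More than one level is met by 4 + 2 = 6 of 9 (exclusive) or 4 + 3 = 7 of 9 (nested).
- The remaining 9 − 5 = 4 profiles, with interference and consequence both present, cannot be Mild.

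**Changing only 'and/or' to 'and' in Mild.** Mild-eligible profiles fall from 5 to 1, and overlaps with Mild fall from 4 to 0. Moderate and Severe still overlap in 2 of 9 (exclusive) or 5 of 9 (nested).

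**Adding a highest-level rule.** Each profile then has one level on either reading: 1 Mild + 3 Moderate + 5 Severe = 9. The highest-level rule alone would give the same mapping, but the Mild definition would still say something that the rule overrides.

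**The case against.** The strongest case against is that the effect is narrow. The primary criterion counts subjects with an ADR whatever its intensity, so it does not move. SAP 5.6.2.1 also reports seriousness, outcome, targeted medication, other targeted action and mixture withdrawal separately from intensity. The AE listings in SAP 5.6.2.4 show intensity beside these items, so a consequential reaction labelled Mild stays visible. The wording permits Mild without requiring it, so a downward shift is possible but not shown. No comparison of sites is planned: SAP 3.7 provides only the number of patients per center. The glue breakdowns exist, but nothing suggests that the wording acts differently by glue. All of this stands, and it limits the point to the intensity breakdowns. It does not remove the overlap or supply a tie-break. Nor do the serious-ADR tables replace the grade, because protocol 10.2.1 treats severity and seriousness as different things.

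A reader might go further and infer that any reaction in the catheterization laboratory can be graded Mild whatever its consequence, since nobody pursues daily activities on the table. The documents do not support that:

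- Mild also requires that the subject is aware of the sign or symptom.
- SAP 5.6.2.1 places an ADR in the primary window by its start, while protocol 10.1.2 has AEs followed to resolution or stabilization. A reaction that begins on the table and later limits the subject does interfere with daily activities.
- If such a reaction also has clinical consequence, it falls among the four profiles that cannot be Mild.

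**Conclusion.** The point holds as a defect in the grading definitions. Four of nine profiles can be graded Mild while meeting a higher level. Counting the Moderate/Severe overlap too, six of nine (exclusive reading of Moderate) or seven of nine (nested reading) meet more than one level, with no rule to choose between them. The intensity breakdowns of ADRs and AEs can be inconsistent and may understate severity. The primary count of subjects with an ADR and the serious-ADR counts are unaffected.

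The result assumes a literal reading of 10.1.3, a subject who is aware of the sign or symptom, and no grading rule in material that is not visible, such as eCRF guidance or redacted SAP pages. The nine profiles are kinds of event, not frequencies. The documents do not show how often each would occur, so the counts cannot be turned into a share of ADRs misgraded.

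**What to change.** In protocol 10.1.3 and the eCRF guidance:

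1. Define Mild as no interference with usual daily activities AND no clinical consequence, keeping the awareness condition.
2. Add: if more than one level applies, the highest is recorded.

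Both are worth making. The first removes every overlap with Mild; the second settles the remaining overlap between Moderate and Severe.

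A separate rule that grades in-laboratory reactions on clinical consequence alone is not advised. It would ignore interference that develops later, and it would mix two scales in the SAP 5.6.2.4 tables that run from first administration to the end of follow-up.

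The change needs a few words, with no new visit. The Mild share may look less favourable. Events already graded may need a check: the SAP is dated June 2021 and carries COVID-19 withdrawal rules, which suggests that subjects had already been enrolled.
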